**ADVERSE EVENTS**

Adverse Event Definition:
An Adverse Event (AE) is defined as any new untoward medical occurrence or worsening of a preexisting medical condition in a clinical investigation participant administered study drug and that does not necessarily have a causal relationship with this treatment.
An AE can therefore be any unfavorable and unintended sign (such as an abnormal laboratory finding), symptom, or disease temporally associated with the use of study drug, whether or not considered related to the study drug.

## SERIOUS ADVERSE EVENTS

Serious Adverse Event (SAE) is defined as any untoward medical occurrence that, at any dose:

Results in death

Is life-threatening (defined as an event in which the participant was at risk of death at the time of the event; it does not refer to an event which hypothetically might have caused death if it were more severe)

Requires inpatient hospitalization or causes prolongation of existing hospitalization (see NOTE below)
 
NOTE:
 
The following hospitalizations are not considered SAEs in BMS clinical studies:
 
 
○ a visit to the emergency room or other hospital department < 24 hours, that does not result in admission (unless considered an important medical or life-threatening event)
 
○ elective surgery, planned prior to signing consent
 
○ admissions as per protocol for a planned medical/surgical procedure
 
○ routine health assessment requiring admission for baseline/trending of health status (e.g., routine colonoscopy)
 
○ medical/surgical admission other than to remedy ill health and planned prior to entry into the study. Appropriate documentation is required in these cases
 
○ admission encountered for another life circumstance that carries no bearing on health status and requires no medical/surgical intervention (e.g., lack of housing, economic inadequacy, caregiver respite, family circumstances, administrative reason)
 
○ admission for administration of anticancer therapy in the absence of any other SAEs (applies to oncology protocols)
 

Results in persistent or significant disability/incapacity

Is a congenital anomaly/birth defect

is an important medical event (defined as a medical event(s) that may not be immediately life-threatening or result in death or hospitalization but, based upon appropriate medical and scientific judgment, may jeopardize the participant or may require intervention [e.g., medical, surgical] to prevent one of the other serious outcomes listed in the definition above.) Examples of such events include, but are not limited to, intensive treatment in an emergency room or at home for allergic bronchospasm; blood dyscrasias or convulsions that do not result in hospitalization.) Potential drug induced liver injury (DILI) is also considered an important medical event. (See Section 8.1.1 for the definition of potential DILI.)

Suspected transmission of an infectious agent (e.g., pathogenic or nonpathogenic) via the study treatment is an SAE.

Although pregnancy, overdose, cancer, and potential drug induced liver injury (DILI) are not always serious by regulatory definition, these events must be handled as SAEs. (See [Section 9.2.5](#) for reporting pregnancies).

In this study, the following events are study endpoints, per 21CFR 312.32 (c)(5), they are excluded from being reported as an SAE UNLESS the events are related to study drug.

- Death
- Hospitalization prolongation
- ICU admission
- Ventilator use
- Vasopressor use
- Dialysis use

These events will be recorded on other CRF pages instead of the SAE pages.

Any component of a study endpoint that is considered related to study therapy should be reported as SAE (e.g., death is an endpoint, if death occurred due to anaphylaxis, anaphylaxis must be reported).

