## **9.2 Adverse Events**

The definitions of an AE or serious adverse event (SAE) can be found in [Appendix 3](#).

AEs will be reported by the participant (or, when appropriate, by a caregiver, surrogate, or the participant's legally authorized representative).

The investigator and any designees are responsible for detecting, documenting, and reporting events that meet the definition of an AE or SAE and remain responsible for following up AEs that are serious, considered related to the study treatment or the study, or that caused the participant to discontinue before completing the study.

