### **9.2.2 Time Period and Frequency for Collecting AE and SAE Information**

The collection of nonserious AE information should begin at initiation of study treatment at the time points specified in the Schedule of Activities ([Section 2](#)) and for a minimum of 90 days following discontinuation of study treatment. Every adverse event must be assessed by the investigator with regard to whether it is considered immune-mediated. For events which are potentially immune-mediated, additional information will be collected on the participant's case report form. Nonserious AE information should also be collected from the start of a placebo lead-in period or other observational period intended to establish a baseline status for the participants.

Sections 5.6.1 and 5.6.2 in the Investigator Brochure (IB) represent the Reference Safety Information to determine expectedness of serious adverse events for expedited reporting. Following the participant's written consent to participate in the study, all SAEs, whether related or not related to study drug, must be collected, including those thought to be associated with protocol-specified procedures.

All SAEs must be collected that occur during the screening period and within 90 days of discontinuation of dosing.

- Medical occurrences that begin before the start of study treatment but after obtaining informed consent will be recorded on the appropriate section of the eCRF section.
- All SAEs will be recorded and reported to Sponsor or designee within 24 hours, as indicated in [Appendix 3](#).
- The investigator will submit any updated SAE data to the sponsor within 24 hours of this being available.

Investigators are not obligated to actively seek AEs or SAEs in former study participants. However, if the investigator learns of any SAE, including a death, at any time after a participant has been discharged from the study, and he/she considers the event reasonably related to the study treatment or study participation, the investigator must promptly notify the sponsor.

The method of evaluating, and assessing causality of AEs and SAEs and the procedures for completing and reporting/transmitting SAE reports are provided in [Appendix 3](#).

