## REPORTING OF SAES TO SPONSOR OR DESIGNEE

- SAEs, whether related or not related to study drug, and pregnancies must be reported to BMS (or designee) within 24 hours of awareness of the event.
- SAEs must be recorded on the SAE Report Form; pregnancies on a Pregnancy Surveillance Form (electronic or paper forms).
- The preferred method for SAE data reporting collection is through the eCRF.
- The paper SAE/pregnancy surveillance forms are only intended as a back-up option when the eCRF system is not functioning.
  - In this case, the paper forms are to be transmitted via email or confirmed facsimile (fax) transmission to:

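### Does the Appendix 3 exemption of unrelated endpoint events from SAE reporting make the planned SAE tables unsafe to read?

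*Protocol*

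**What the plan says.** Protocol 9.2 gives no SAE definition of its own: "The definitions of an AE or serious adverse event (SAE) can be found in" Appendix 3. Protocol 9.2.2 then requires that "all SAEs, whether related or not related to study drug, must be collected", and adds: "All SAEs will be recorded and reported to Sponsor or designee within 24 hours, as indicated in" Appendix 3.

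The Serious Adverse Events part of Appendix 3 gives the usual seriousness criteria, including a fatal outcome and prolongation of a hospital stay. It then names six events as endpoints of this study and states that "they are excluded from being reported as an SAE UNLESS the events are related to study drug". On where they go: "These events will be recorded on other CRF pages instead of the SAE pages". On related events: "Any component of a study endpoint that is considered related to study therapy should be reported as SAE", with anaphylaxis leading to death as the example.

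The reporting part of the same appendix says: "SAEs, whether related or not related to study drug, and pregnancies must be reported to BMS (or designee) within 24 hours of awareness". It does not mention the exception.

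SAP 4.1 names SAEs and deaths as separate components of the primary safety endpoint. SAP 7.7.2 plans a table of on-treatment SAEs, a table of drug-related SAEs, versions restricted to higher grades including grade 5, and a listing of every SAE. It does not refer to the exemption. SAP 7.7.1 lists all deaths after consent and tabulates them from any cause, by arm and in total.

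**The concern.** Two rules in the protocol cover unrelated SAEs without exception, and a third removes six types of event from SAE reporting when they are unrelated. Read literally, the first two would put an unrelated sepsis death on the SAE pages and the third would keep it off.

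If the exemption is applied, the main SAE table looks as if it covers events regardless of causality, yet for the exempt types it holds only those judged related. For those types it then matches the drug-related table. The grade 5 SAE count can fall below the death count in SAP 7.7.1, and the SAP does not say why. Appendix 3 also does not say how to record the diagnosis behind an unrelated exempt event, so two sites could handle the same case differently. In an ICU population with severe sepsis, deaths and organ support are foreseeable, and SAE incidence is a primary safety measure. A reader might therefore fear that the measure is understated.

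**Working it through.** No figure in the plan is in dispute, so the check is mainly a comparison of texts.

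**1. Which rule governs.** Section 9.2 hands the definition to Appendix 3, and 9.2.2 hands over the reporting procedure. The exemption is a study-specific statement inside that definition. The later reporting rule sets timing and forms for whatever counts as an SAE. Its reference to unrelated events still has content, because unrelated SAEs outside the six exempt types must be reported. The specific statement limits the general one, and the texts can be applied together.

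**2. What is exempt.** The six items are an outcome (death), two measures of care (prolonged stay, ICU admission) and three interventions. The SAE tables count coded preferred terms, which are mostly diagnoses. Under the seriousness criteria, an occurrence that is fatal or life-threatening is itself an SAE, and the exemption does not expressly remove the diagnosis. The text is silent on the unrelated case, so the grade 5 SAE count may fall below the death count, but need not. AEs are defined "whether or not considered related to the study drug", so an underlying diagnosis recorded as an AE appears in the tables of SAP 7.7.4, which also have a version showing grade 5.

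**3. Where the exempt events are reported.**

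| Exempt event | Reported in |
|---|---|
| Death | SAP 7.7.1, all causes, by arm and total; Protocol 9.4, mortality at 28 and 90 days and time to death |
| Ventilator, vasopressor, dialysis use | SAP 7.6.1, durations in the index hospitalization, with listings |
| Prolonged stay, ICU admission | SAP 7.6.1, ICU and hospital length of stay in the index hospitalization, with listings |

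Organ support and ICU stay after index discharge have no named page. A new inpatient admission, however, remains a seriousness criterion and is not on the exempt list; only prolongation of a stay is. A readmission that includes ICU care therefore still enters as an SAE.

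**4. Decisions during the study.** Protocol 8.4 has three criteria for pausing enrollment. The mortality criterion does not depend on SAE coding. The repeated-SAE criterion requires relatedness, and related events are not exempt. Potential drug-induced liver injury must be handled as an SAE in any case. The exemption alters none of the three.

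**5. Unit effect.** SAP 5 gives up to about 15 participants per arm, so about 30 in total. For one participant whose only serious event is exempt and unrelated:

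- within the arm: 1/15 = 0.067, or 6.7 percentage points;
- in the total column: 1/30 = 0.033, or 3.3 percentage points.

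This is the weight of any single participant in a trial of this size. It does not measure how often the situation arises. The documents give neither expected mortality nor how often an exempt event would be a participant's only serious event. If the underlying diagnosis is always reported as an SAE, the effect is zero.

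**The case for a change.** The strongest point is that the reporting rule lies in the same appendix as the exemption and still omits it, and that what it omits concerns relatedness, the criterion on which the exemption turns. Sites could in good faith record the diagnosis behind an unrelated death in different ways, and the SAP gives a reader no label to explain a difference between grade 5 SAEs and deaths. A cross-reference, a recording sentence and a footnote would cost little. One could also add a table of participants with any SAE or death.

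The omission stands as a fact about the text, and so does the silence on recording the diagnosis. What does not stand is the step from there to a distorted endpoint: the counts may differ, but the documents do not show that they do. The cross-reference largely exists already, through 9.2 and 9.2.2. A footnote belongs to table production, which SAP 7.7.2 leaves to standard layouts; those are not available here and may already carry one. A combined table would cover only one of the six exempt types, and with about 30 participants it can be derived from the SAE and death listings already planned.

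**Conclusion.** No change to the plan follows. This is a gap in wording that sites and analysts can fill by reading Appendix 3 as the protocol directs. Keeping expected outcomes of sepsis off the SAE pages unless they are drug-related is a deliberate study-specific rule, and the deaths it moves are reported in full elsewhere as a primary measure.

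The effect on SAE incidence is of unknown size and may be zero; its unit is 6.7 points per arm and 3.3 points overall at the planned maximum, and more if fewer are treated. Both arms receive nivolumab, the investigators who judge causality are blinded to dose (Protocol 7.3, SAP 7.7), and the sample size is not based on power (SAP 5), so no between-arm bias is shown and no test is at risk.

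This rests on two assumptions: that sites apply the exemption as Appendix 3 states it, and that SAE and death outputs are read together, as the primary endpoint's separate naming of the two invites.

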Procedure	WK 1 D1-7	WK2 D10	WK2 D14	WK3 D21	WK4 D28	WK6 D42	WK8 D56	WK10 D70	Indexa Hospitaliza tion Discharge	Studyb Discharge D90	Notes
											procedures.
Electrocardiogram (ECGs)	X		X		X		X		X	X	Perform at end of infusion on Day 1, at Index Hospitalization Discharge, and at Study Discharge; Perform at other time points only if still hospitalized.
Clinical safety laboratory tests	X	X	X	X	X		X		X	X	Days 1, 4 and 7 of week 1. See note in screening procedures and in Section 9.4.4
Pregnancy Test					X		X			X	WOCBP only. See note in Section 9.4.4.
Thyroid function testing							X		X	X	See note in Section 9.4.4
Adverse Event Reporting											
Monitor for Non-Serious Adverse Events	Collection of nonserious adverse events begins at initiation of study treatment. Adverse events must be collected up to Day 90.										
Monitor for Serious Adverse Events	See note in Screening procedures. SAEs must be collected up to Day 90.										
Other Assessments											

Table 2.-2: On Treatment Procedural Outline (CA209923)											
Procedure	WK 1 D1-7	WK2 D10	WK2 D14	WK3 D21	WK4 D28	WK6 D42	WK8 D56	WK10 D70	Indexa Hospitaliza tion Discharge	Studyb Discharge D90	Notes
Ventilator Usage	In days counting from the day of study treatment administration during participant’s index hospitalization.										
Vasopressor Usage	In days counting from the day of study treatment administration during participant’s index hospitalization.										
Dialysis Usage	In days counting from the day of study treatment administration during participant’s index hospitalization.										
Mortality	Date and primary cause of death.										
SOFA Score	Daily during the first week after study treatment administration, and weekly thereafter while participant is in ICU during participant’s index hospitalization.										
Length of ICU stay During Index Hospitalization	ICU discharge date during index hospitalization.										
Length of Index Hospitalization	Hospital discharge date during index hospitalization.										
Pharmacokinetic (PK) and Immunogenicity Assessments	See Section 9.5 for details and collection schedule.										

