#### 2) Type of Participant and Target Disease Characteristics

- a) Men and women ages  $\geq 18$  years old
- b) Participant has documented OR suspected infection
  - i) Documented infection is infection confirmed with a microbiologic diagnosis
  - ii) Suspected infection is infection being treated with ongoing antimicrobial therapy at the time of study treatment administration
- c) Participant has the onset of severe sepsis or septic shock at least 24 hours prior to study treatment administration based on having at least 1 of the 3 organ dysfunction criteria below. Organ dysfunction must be new and thought to be due to sepsis.
  - i) Hypotension defined as the need for treatment with any vasopressor(s) for at least 6 hours to maintain a systolic pressure  $\geq 90$  mmHg or a mean arterial pressure  $\geq 70$  mmHg  
OR
  - ii) Acute respiratory failure defined as the need for invasive mechanical ventilation for at least 24 hours to support pulmonary function  
OR
  - iii) Acute kidney injury defined as creatinine  $> 2.0$  mg/dL (from a creatinine that was within the normal reference range prior to onset of sepsis) OR urine output  $< 0.5$  mL/kg/hr for  $> 2$  hours despite adequate fluid resuscitation. In the presence of pre-existing impairment of renal function (defined as a serum creatinine concentration  $> 2$  times the upper limit of the normal reference range prior to the onset of sepsis), the participant should meet 1 of the other 2 organ dysfunction criteria above.
- d) Participant has sepsis-associated immunosuppression based on an absolute lymphocyte count  $\leq 1100$  cells/ $\mu$ L on at least one assessment within the 96 hours prior to study treatment administration
- e) Participant is in an intensive care unit at the time of study treatment administration and, based on their medical condition, there are no plans to discharge from the ICU in the next 24 hours
- f) Participant Re-enrollment: This study permits the re-enrollment of a participant who has discontinued the study as a pre-treatment failure (ie, participant has not been randomized /has not been treated). If re-enrolled, the participant must be re-consented.

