#### **9.1 Efficacy Assessments**

Exploratory efficacy assessments include the following:

- Organ failure will be assessed by collection of SOFA score during index hospitalization

- Organ support will be assessed by duration of mechanical ventilation, vasopressor use, or dialysis use separately during the index hospitalization
- Length of stay in the ICU and in the hospital during the index hospitalization will be assessed

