7.6 Efficacy

7.6.1 Exploratory Efficacy

Summary statistics will be provided for the following assessments by treatment and periodic time points. Listings will also be provided.

- Duration of mechanical ventilation, vasopressor use, or dialysis use separately during the index hospitalization.
- Sequential organ failure assessment (SOFA) scores at baseline and post-dosing time points, and change from baseline of SOFA scores during the index hospitalization.
- Length of ICU and hospital stay during index hospitalization.

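### The Appendix 3 exemption of unrelated ICU and organ-support events from SAE reporting has no end date, while the data meant to replace those reports end at index hospital discharge

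*Protocol*

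**What the plan says.** Protocol Appendix 3 (Serious Adverse Events) lists six study endpoints: death, prolonged hospitalization, ICU admission, and ventilator, vasopressor and dialysis use. Of these it says "they are excluded from being reported as an SAE UNLESS the events are related to study drug", and then "These events will be recorded on other CRF pages instead of the SAE pages". It states no period for the exemption.

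Elsewhere the plan sets these periods:

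- **SAE collection.** Table 2.-2 says "SAEs must be collected up to Day 90". Section 9.2.2 requires every SAE to be collected whether or not it is related.
- **Organ support.** Table 2.-2 records ventilator, vasopressor and dialysis use "In days counting from the day of study treatment administration during participant’s index hospitalization". Section 9.1 says "Organ support will be assessed by duration of mechanical ventilation, vasopressor use, or dialysis use separately during the index hospitalization", Section 9.8.7 repeats this, and SAP 7.6.1 analyses "Duration of mechanical ventilation, vasopressor use, or dialysis use separately during the index hospitalization".
- **ICU stay.** The only item in Table 2.-2 is "ICU discharge date during index hospitalization".
- **CRF content.** Section 9.4 restricts CRF data to protocol-specified assessments, unless the sponsor specifically asks for more.

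Inclusion criterion 2e adds "Participant is in an intensive care unit at the time of study treatment administration". Footnote a to Table 2.-2 allows index discharge at any time after dosing.

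**The concern.** Exempting expected endpoint events from SAE reporting is reasonable when they are captured somewhere else. Here the exemption covers the whole study, but the scheduled capture stops at index discharge, which may come well before Day 90. Within the index stay, the exempted ICU admission has no matching scheduled item once a participant has been dosed: everyone is already in the ICU at dosing, so a later admission is a readmission, and only a discharge date is scheduled.

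At stake is consistent counting of SAE incidence, a primary endpoint in Protocol Table 4.-1 and SAP 4.1. The trial compares two active doses, with about 15 participants each and no control arm. The exemption depends on a physician's related or not-related call, which is hard to make in critically ill patients. Counting events the same way at every site, regardless of attribution, is the natural check on that call.

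**Working it through.** **The plan's own figure.** Protocol 10.1 and SAP 5 give an 80% chance of seeing at least one event of 10% incidence among 15 participants. 1 − 0.9^15 = 1 − 0.206 = 0.794, so the figure is reproduced. The present point does not depend on it.

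**The rules side by side, for events judged unrelated.**

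| Event | Appendix 3 exemption | Scheduled replacement item | Other route in the plan | What is left |
|---|---|---|---|---|
| Organ support during the index stay | Applies | Days of each type, Table 2.-2 | SAP 8.2 defines separate ventilation episodes | No gap |
| ICU readmission during the index stay | Applies | ICU discharge date only | Organ support in that readmission is still counted | No scheduled readmission date; SAP 8.2 has no rule for a second ICU stay |
| Dialysis started or continued as an outpatient after discharge | Applies | None; SAP 8.2 censors renal support at hospital discharge | The underlying kidney event can still be an AE to Day 90 | Dialysis itself has no item |
| Vasopressor after discharge | Applies | None | Concomitant therapy on the CRF (7.8.1; SAP 7.5.2) | The drug is recorded; SAE status is unclear |
| ICU admission or ventilation after discharge | Applies by its wording | None | A new inpatient admission or life-threatening event meets the general SAE definition | Two rules conflict |
| Death | Applies | Date and cause, with no index-stay limit | – | No gap |

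**The conflict.** Suppose a participant goes home and is later admitted directly to an ICU for a reason judged unrelated. The general SAE definition in Appendix 3 makes the inpatient admission an SAE, and Section 9.2.2 requires it to be collected. The exemption list names prolonged hospitalization but not a new admission. It does name ICU admission, without a period. One site can reasonably file an SAE and another can reasonably treat the episode as exempt. At the second site the replacement data have already ended.

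**Length of the period concerned.** The documents give no discharge dates. As an assumption, take index discharge at Day 14, 28 or 56:

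- 90 − 14 = 76 days (76/90 = 84%)
- 90 − 28 = 62 days (62/90 = 69%)
- 90 − 56 = 34 days (34/90 = 38%)

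These are the days on which the exemption applies and no dedicated ICU or organ-support item is scheduled. They measure exposure to the unclear rule, not a number of missed events.

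**The case against.** The strongest reply is that little is actually lost. After discharge, ICU care or ventilation would ordinarily involve a new inpatient admission, which remains an SAE criterion and is not on the exemption list. Life-threatening events also remain SAEs. The exemption names interventions and levels of care, not the illness behind them, so new respiratory failure, shock or kidney injury can still be reported as an AE to Day 90. Organ support during an ICU readmission in the index stay is counted. The index-stay window belongs to exploratory efficacy measures, and the CRF itself is not among the documents.

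Most of this stands. A reader might infer that late organ failure goes entirely unrecorded, and the documents do not support that, for the reasons just given. A reader might also infer that the sponsor's enrolment-pause rules are weakened. They are not: the triggers in Section 8.4 are unusual mortality, repeated unexpected SAEs judged related, and potential drug-induced liver injury, and an unrelated ICU or organ-support event in itself meets none of them. Nor does the ICU item refer only to readmissions. SAE collection starts at consent and ICU status is required only at dosing, so a first ICU admission can fall inside the SAE period.

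What the reply does not remove is the mismatch of periods. The CRF pages may be wider than the schedule, but Section 9.4 gives no ground for assuming so.

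**Conclusion.** The point holds in limited form. The exemption outlasts the data meant to justify it, leaving three gaps: outpatient dialysis after discharge, undated ICU readmissions within the index stay, and post-discharge ICU or organ-support episodes on which the exemption and the general SAE rules disagree. The consequence is possible inconsistency between sites in a primary safety endpoint, not a wholesale loss of late events.

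The number of affected participants cannot be given. It would need rates of discharge, readmission and outpatient dialysis, and the share of episodes that sites would treat as exempt; the documents supply none of these. An assumed readmission rate would count episodes that occur, not episodes that go unreported. The conclusion rests on the CRF following the Schedule of Activities. This is a cheap improvement and does not undermine the design.

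**What to change.** 1. In Protocol Appendix 3, limit the exemption of ICU admission and ventilator, vasopressor and dialysis use to the index hospitalization. State that after index discharge these events follow the general SAE definition to Day 90, consistent with Section 9.2.2. The item for death needs no such limit, because its date and cause are recorded without one.
2. In Table 2.-2, record every ICU admission and discharge date during the index hospitalization.
3. Optionally, add to SAP 7.7 a count of participants with a new ICU admission or newly started organ support after dosing, by treatment and total. After discharge this count would draw on SAE reports, since no structured field would exist.

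Outpatient dialysis would then be judged against the general SAE criteria. That removes the blanket exemption but does not guarantee a record for every dialysis course; if dialysis status after discharge is wanted for everyone, it needs its own item.

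The cost of the first two changes is one sentence, one CRF field and a few more SAE reports from sites after discharge. Only reporting changes.
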